#### Study Procedures:

**Screening & Enrollment:** All patients 18 years or older presenting for initial treatment, nonunion or limb length deformity correction of the femur, tibia (plateau, shaft, pilon), or hindfoot/ankle will be screened for eligibility. Once eligibility has been confirmed, a research coordinator and/or investigator will approach patient for consent prior to surgery. Patients will be given the opportunity to review the informed consent document and ask questions about the study. The informed consent will comply with the ICH/GCP regulatory guidelines.

**Baseline:** Once consent is obtained, baseline data regarding participant characteristics, injury characteristics and PROMIS scores will be collected from the participant and entered into the electronic data collection system. Data will also be collected from the medical record regarding injury characteristics, fracture fixation, pain scores and utilization of pain alleviation modalities (pharmaceutical and nonpharmaceutical).

**Follow-up:** Participants will complete study visits at 2, 6, and 12 weeks following admission to the hospital, which may overlap with regularly scheduled standard of care clinic visits. These visits may also be completed via phone calls, text messages, or email. At these visits, participants will be asked to complete PROMIS-29 survey. Data regarding use of any pharmaceutical and nonpharmaceutical modalities for pain management will be collected at these visits. Additional variables about fracture complications will be collected from the electronic medical record.

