## Transcutaneous Electrical Nerve Stimulation (TENS) for Pain Alleviation in Perioperative Fracture Patients

### Specific Aims:

Opioid overdoses continue to increase, and the path to addiction often begins with a prescription. Half of postoperative patients receive an opioid prescription. Multimodal pain management, including cognitive, physical, and pharmaceutical strategies, reduces reliance on opioids alone. Transcutaneous nerve stimulation (TENS) is one physical strategy; this study aims to evaluate the effectiveness of TENS as part of postoperative pain management.

**Specific Aim 1:** To pilot the use of TENS among a postoperative lower extremity injury population as part of multimodal pain management.

$H_0$ : TENS cannot be delivered safely among this population.

$H_A$ : TENS can be delivered safely among this population.

**Specific Aim 2:** To compare utilization of inpatient and outpatient pain medications of patients treated with TENS and historical controls.

$H_0$ : Patients treated with TENS will require the same amount of opioids as historical controls.

$H_A$ : Patients treated with TENS will require less opioids (lower morphine milligram equivalent – MME) than historical controls during hospitalization and throughout 3-month follow up.

**Specific Aim 3:** To compare patient-reported outcomes of patients treated with TENS and historical controls.

$H_0$  1: Patients treated with TENS will experience equivalent patient-reported outcomes as compared to historical controls.

$H_A$  1: Patients treated with TENS will experience greater improvement in patient-reported outcomes (PROMIS 29) relative to baseline as compared to historical controls.

$H_0$  2: Patients treated with TENS will report higher pain scores as compared to historical controls.

$H_A$  2: Patients treated with TENS will report equivalent or lower pain scores as compared to historical controls.

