## **Research Design and Method:**

### Overall Design

This will be a prospective observational study of patients undergoing operative treatment of lower extremity conditions, including fracture fixation, treatment of nonunion, and deformity correction. The study will be conducted at a single Level I trauma center. Enrolled patients will receive TENS postoperatively during hospitalization; TENS units will also be sent home with patients for use throughout recovery. This group will be compared to controls injury-matched from a prospectively collected, historical database on mobility who did not receive treatment with TENS.

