#### Treatment Groups:

The prospectively enrolled patients will have TENS pads placed immediately following surgery, prior to PACU. The TENS unit will be connected to the pads and turned on in the PACU. Each patient will receive instructions for suggested use of the device. They will be allowed to individualize the frequency/amplitude of the current to reach a "strong sub-noxious" stimulation, as recommended by previous studies. They will be asked to aim for 4x45 minute sessions each day. This protocol was previously published by a separate group demonstrating decreased post-operative pain levels with adjunctive TENS use.

This institution has an ongoing research study which collects injury characteristics, patient-reported outcomes, and kinematic/performance data for orthopaedic trauma patients with lower-extremity injuries. Patients with similar injuries as the prospectively enrolled patients will be identified in this database to serve as controls, because TENS units were not previously used at this institution for pain management. Our institution also has a database of all opioid prescriptions as well as risk factors that can be used to provide these data for the controls.

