#### Adverse Reporting

All adverse event will be reported accordance with the local IRB rules. The principal investigator must classify the event as Related, Probably Related, Possibly Related or Not Related.

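### Aim 1 tests safe delivery of TENS, but no listed follow-up item asks about device effects or why use stopped, so harms are likely to be under-counted

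*Protocol*

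**What the plan says.** Under Specific Aims, the alternative hypothesis of Aim 1 is that "TENS can be delivered safely among this population". Overall Design adds to inpatient treatment that "TENS units will also be sent home with patients for use throughout recovery". Treatment Groups sets the target: "They will be asked to aim for 4x45 minute sessions each day", at an intensity the patient adjusts.

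Follow-up is described under Study Procedures. "Participants will complete study visits at 2, 6, and 12 weeks following admission to the hospital", and "These visits may also be completed via phone calls, text messages, or email". The content listed is:

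- "At these visits, participants will be asked to complete PROMIS-29 survey";
- data on drug and non-drug pain modalities used;
- from the chart: "Additional variables about fracture complications will be collected from the electronic medical record".

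Outcome Measures lists opioid use, PROMIS-29 and pain scores as outcomes. Its process measures are compliance at home, sessions per day, session length and stimulation settings. No safety or tolerability outcome appears there.

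Adverse Reporting states that "All adverse event will be reported accordance with the local IRB rules" and has the principal investigator grade each event on a four-level relatedness scale. It does not say how events are to be found, or to what they are to be judged related.

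**The concern.** Safety is the first aim, so the trial needs a way to find events as well as a rule for handling them once found. The follow-up content and process measures would show that a patient used the unit less, but not whether the reason was skin irritation, discomfort, lack of benefit or recovery. A minor problem at a pad site that the patient manages at home may produce no chart entry, and if nobody asks, it may not be mentioned in a text or email contact.

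The error then runs in one direction. Missed events lower the observed rate, and a low observed rate is what would support Aim 1. Later analysis cannot recover answers to questions that were never asked, so this is a data-collection matter for the protocol and not one that a statistical analysis plan could settle.

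Two smaller gaps sit beside it. The control sources named under Treatment Groups list injury characteristics, patient-reported outcomes, performance data, opioid prescriptions and risk factors, but not complications. And home use has no stated end, while the last scheduled contact is at week 12.

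**Working it through.** The protocol gives no figure for safety, so there is none to reproduce. The only number taken from its Sample Size section is the 50 enrolled TENS patients.

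**Step 1: is there an eliciting item?**

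| Place in the protocol | What is captured | Device effect or reason for stopping? |
|---|---|---|
| Study Procedures, Follow-up (patient) | PROMIS-29, pain modalities used | No |
| Study Procedures, Follow-up (chart) | Fracture complications | No |
| Outcome Measures, process measures | Compliance, sessions, duration, settings | No |
| Adverse Reporting | Reporting and relatedness of events | Only after an event is known |

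**Step 2: how much of the planned use is at home?** Target use is 4 × 45 = 180 minutes, or 3 hours a day. Over 12 weeks (84 days) that is 3 × 84 = 252 hours. Length of stay and duration of use are not stated, so both are assumed and varied. With use to day E and a stay of L days, home share = (E − L)/E.

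| Use ends | L = 2 days | L = 7 days |
|---|---|---|
| Week 12 (E = 84) | 82/84 = 97.6% | 77/84 = 91.7% |
| Week 6 (E = 42) | 40/42 = 95.2% | 35/42 = 83.3% |
| Week 2 (E = 14) | 12/14 = 85.7% | 7/14 = 50.0% |

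This counts use from admission. The pads go on after surgery, so any days before surgery would raise the home share slightly.

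**Step 3: what does incomplete capture do?** Let p be the true proportion of patients with a device effect and c the proportion of those that get recorded. Then P(at least one recorded in 50) = 1 − (1 − pc)^50. With p = 5% (assumed):

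- c = 100%: 1 − 0.95^50 = 92%
- c = 50%: 1 − 0.975^50 = 72%
- c = 25%: 1 − 0.9875^50 = 47%

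**Step 4: how would zero recorded events be read?** The one-sided 95% upper bound is 1 − 0.05^(1/50) = 5.8%. That bounds p only if c = 100%. Otherwise it bounds pc, and the bound on p is 5.8%/c: 5.8/0.50 = about 12% at half capture and 5.8/0.25 = about 23% at quarter capture.

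The values of p and c are illustrations. The protocol supplies neither.

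**The case against.** The strongest reply is that the protocol already has a route for harms. Adverse Reporting covers every adverse event, whatever its source, so a problem volunteered at any contact is reported and graded. Compliance data would reveal stopping or reduction. Remote contact is permitted, not required: pill counts at follow-up visits and clinic pain scores imply that many patients will be seen. Prompts may also sit in case report forms that are not shown, and the protocol describes TENS as a non-significant-risk device.

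This rules out several stronger readings that a reader might infer:

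- *Device harms would go unrecorded, leaving false zeros.* Spontaneous reports and chart entries will catch some. Even at half capture, the illustration leaves a 72% chance of at least one recorded event.
- *Complications are collected for enrolled patients only.* The sentence sits under participant follow-up, but nothing excludes chart review for controls at the same institution. What can be said is that no control source is named.
- *Harms could not be attributed to TENS.* Case-by-case grading needs no control rate, and pad-site effects cannot occur in untreated controls. Nor would a control rate separate much: at assumed complication rates of 10% and 20%, 50 against 50 has about 29% power (normal approximation).
- *Nearly all use is unsupervised at home.* The home share depends on an unstated duration of use and could be as low as 50% in the cases above. The protocol also tracks sessions and compliance, so self-directed is the fairer word.

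What the reply does not meet is the absence of any listed question. Reporting and grading both come after detection, and compliance data show a change in use without its cause.

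**Conclusion.** The point holds as one of likely under-ascertainment. For its first aim, the protocol as written relies on spontaneous report and chart entries during a period in which at least half of target use falls at home in every case examined (assumed stay of 2 to 7 days, use ending at week 2, 6 or 12). The resulting bias favours a conclusion of safety. Its size cannot be fixed from the document. Under an assumed 5% true rate, the chance of recording any event in 50 patients is 92%, 72% or 47% at full, half or quarter capture.

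The missing control source and the open-ended period of use are secondary. The first limits context for ordinary postoperative complications. The second is a gap between Overall Design and Study Procedures, and does not show that use will continue after monitoring ends.

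**What to change.** Add a short fixed set of questions to the existing 2-, 6- and 12-week contact form, asked in the same words whether the contact is in person or remote:

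1. any problem at the pad sites;
2. any discomfort or event during use;
3. any stop or reduction in use, and why.

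Route every positive answer to the classification under Adverse Reporting, and state there that relatedness means related to TENS.

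State that the same fracture-complication variables will be abstracted from the record for the matched controls over the same postoperative window, as descriptive context and not as a test.

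The sponsor should reconcile the open-ended home use in Overall Design with the week-12 last contact in Study Procedures. How to do so is the sponsor's decision.

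The cost is a few questions on contacts that already take place, more minor events to log, and some added chart abstraction for the 50 controls.

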#### Adverse Reporting

All adverse event will be reported accordance with the local IRB rules. The principal investigator must classify the event as Related, Probably Related, Possibly Related or Not Related.

